Screening/Data Collection Description: The anticipated process for the screening and data collection is as follows and expected to take 45 minutes. After obtaining consent via the digital informed consent tool on the iPad, the RA will assist the older adult with putting on the headphones; orient them to the iPad screen, and explain the process that will follow. First, participants will complete a demographic pre-survey. Next, they will begin VOICES with an interactive educational session about EM and APS response, and will be screened for EM. For participants who screen positive, VOICES will ask them if they would like to self-disclose. If they choose to disclose VOICES will stop and thank them for participating. If they choose not to disclose EM, they will then complete the BNI and be asked again if they would like to self-disclose.

VOICES is not intended to replace the existing protocols for handling EM in EDs. Rather it is intended to help screen and identify cases of suspected EM that otherwise will be missed. The established protocol at YNHHS when EM is suspected requires notifying the ED social worker who will conduct an in-person evaluation and decide on the best approach to handle the case. VOICES will first screen for EM and administer an interactive educational session. It will then ask if the older adult would like to self-Identify with EM. If the patient does not want to self-identify, VOICES will administer BNI and ask again if the older adult want to self-identify with EM. If the patient chooses to identify with EM, the research assistant (RA) will notify the provider/social worker and say, "The patient wants to disclose EM". When the older adult is finished they will signal to the RA who will collect the iPad, complete a brief post-survey, administer the \$20.00 incentive and (if needed) will notify their provider.

[figure not shown]

Figure 3: High Level Flow Chart of VOICES

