Demand	To what extent is VOICES likely to be used?	Size of target population of EM victims in the ED measured by % who screen positive for EM and % who receive the BNI portion of VOICES
Implementation	To what extent can VOICES be delivered to participants in the defined, but not fully controlled, context of the ED?	Degree of execution measured by % of potential participants approached who consent to participate in the pilot study Success of execution measured by # of participants who used the tool to completion and reasons for not completing the tool as reported on post-survey
Practicality	To what extent can VOICES be carried out with intended participants without outside intervention?	Efficiency of implementation measured by the average time (1) to consent & orient participants to the tool and (2) needed to complete VOICES documented by the RA; and (3) patients perceived time of VOICES as measured on post-survey Factors affecting implementation measured by the number and source of interruptions during participation documented by the RA; The number of participants who want their caregiver/family member present during study as documented by the RA Positive/Negative effects of VOICES measured by participants' perceptions of safety concerns vs. benefits as reported on post-survey
Limited Efficacy	Does VOICES show promise of being successful?	Observed trends in proportions of reported (1) portion of participants who change their self-identification response after completing the education (2) portion of participants who change readiness to disclose after completing the BNI (3) exploration of whether self-identification impacts likelihood of self-disclosure Effect-size estimation measured by change in the % of patients who disclose Potential sources of bias measured by (1) sample representativeness & (2) observed group differences of participants measured by demographic data determine through t-tests and chi-square analyses

Table 1: Planned Data Analyses and Interpretation

Data Management. Study data will be entered into the VOICES by the patients through direct use and by the RA through data entry. We will use VOICES Back-end for the study management needs.

SPECIFIC AIM 3: Exploratory Aim: To perform a preliminary evaluation of the accuracy of VOICES as a screening tool in correctly classifying EM cases that were referred to Adult Protective Services (APS).

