Connecticut law requires reporting of the abuse of persons above the age of 60. During the consent process, participants will be notified of this legal requirement but reassured that investigators will make every effort to make the process confidential and comfortable for the participant, including a) keeping the participant's reporting confidential and b) involving the care team (clinician, nurses, and attendings), who can address patient's concerns around reporting, immediate safety concerns, and any concerns for retaliation or abandonment.

At the end of the consent process, the RA will review the subject's understanding of the study by asking the following question:

- What are you being asked to do?
- What questions is this study trying to answer?
- What are the potential risks and benefits of participating in this study?
- Can you withdraw from the study, and what should you do if you decide to withdraw?
- Do you understand that participation in this study is voluntary and is not part of your medical treatment?

10. **Risks:** Describe the reasonably foreseeable risks, including risks to subject privacy, discomforts, or inconveniences associate with subjects participating in the research.

There are no medical interventions in this study, the direct medical risks are minimal. However, identification of potential EM without adequate safeguards could increase the risk of physical harm, emotional harm, risk of neglect, and financial loss to the victim. In addition, EM Identification can potentially lead to adverse events

including:

- retaliation of a family member,
- an older adult may lose the caregiver or be abandoned by a caregiver, a family member or paid caregiver may be arrested / incarcerated.
- discharge of a patient to a long-term care or skilled nursing facility, which they may not be able to afford and the setting of which could be problematic for them,
- distress/anxiety during and/or after using the VOICES tool is a potential risk given the complex emotions typically associated with this phenomenon,
- participant may suffer from distress and/or anxiety when reviewing information and answer questions about EM during the study session,
- participant may suffer from distress and/or anxiety when he or she realizes that he she is a victim of EM based on the information received from VOICES,

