4. OUTCOMES

The primary and Other Pre-Specified Outcome Measures are summarized in Table 1.

Table 1. Primary and Other Pre-Specified Outcome Measures		
Domain	Measure (P,O)	Source and Frequency
Implementation	Participation. Participation will be determined by the ratio of participants who are successfully enrolled to the total	Study enrollment records

	number of eligible patients. (P)	
	Usage. Usage will be determined by the number of consented participants enrolled in the study who used VOICES to completion (P)	VOICES tool completion records
Acceptability	Participant satisfaction measured using post-use satisfaction survey with two 5-point Likert response set scales, developed by the research team (O)	Self-report, once per participant
Demand	Measured by the % of the patients who self-identified with elder mistreatment and the % who receive the Brief Negotiation Interview (BNI) portion of VOICES.	Measured by VOICES tool, once per participant
	Average time to consent & orient participants to the tool (O)	RA measurement, once per participant
Practicality	Average time needed to complete VOICES (O)	RA measurement, once per participant
	Average time patients perceived time of VOICES	Self-report, once per participant
Efficacy of the Educational Material	Measured as % of participants that change their self-identification response after completing the educational component (O)	Measured by VOICES tool, once per participant
Efficacy of the Brief Negotiation Interview	Measured as % participants that change their self-identification response after completing the educational component (O)	Measured by VOICES tool, once per participant
Efficacy of Self-Identification on Self-Disclosure	Measured as % of patients who disclose among those who self-identified (O)	Measured by VOICES tool, once per participant
Accuracy	Measured as percent of classified EM cases that were positive based on social worker assessment, and those referred to Adult Protective Services (APS). (O)	Measured by the outcome of the social worker assessment and by the outcome APS evaluation.
EM: Elder Mistreatment; BNI: Brief Negotiation Interview; APS: Adult Protective Services		

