4.2 Other Pre-Specified Outcomes

Acceptability: Participant satisfaction will be measured along multiple dimensions using post-use satisfaction survey with two 5-point Likert response set scales, developed by the research team. Scale 1: Likert scale 1-5, where 1= Very Dissatisfied, and 5= Very Satisfied Scale 2: Likert scale 1-5, where 1= Strongly Disagree, and 5= Strongly Agree

Demand: Demand will be assessed through examining how likely will VOICES be used by patients. To do this, the size of target population of EM victims in the ED will be

measured by the % of the patients who self-identified with elder mistreatment and the % who receive the Brief Negotiation Interview (BNI) portion of VOICES.

Practicality: Practicality will be assessed by observing the ease of VOICES use by patients. To do this, a series of steps will be watched to determine the efficiency of implementation measured by the average time (1) to consent & orient participants to the tool and (2) needed to complete VOICES documented by the Research Assistant; and (3) patients perceived time of VOICES as measured on post-survey. Each of these will be reported as part of the overall outcome.

Efficacy of the Educational Material: To understand the efficacy of VOICES in this pilot, we will look at how many participants changed their self-identification response after completing the educational component.

Efficacy of the Brief Negotiation Interview: We will look at how many patients changed their readiness to identify and readiness to disclose after completing the Brief Negotiation Interview (BNI).

Efficacy of Self-Identification on Self-Disclosure: We will explore whether self-identification impacts likelihood of self-disclosure. Effect-size estimation measured by change in the % of patients who disclose among those who self-identified.

Accuracy: To understand the accuracy of the VOICES tool, a preliminary evaluation of the accuracy of VOICES as a screening tool in correctly classifying EM cases that were positive based on social worker assessment, and those referred to Adult Protective Services (APS). The percent correct classification will be reported.

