7.2 Analysis of Other Pre-Specified Outcomes

Acceptability: Participant satisfaction will be measured along multiple dimensions using post-use satisfaction survey with two 5-point Likert response set scales, developed by the research team. Scale 1: Likert scale 1-5, where 1= Very Dissatisfied, and 5= Very Satisfied Scale 2: Likert scale 1-5, where 1= Strongly Disagree, and 5= Strongly Agree. The means and standard deviations will be reported.

Demand: Demand will be assessed through examining how likely will VOICES be used by patients. To do this, the size of target population of EM victims in the ED will be measured by the % of the patients who self-identified with elder mistreatment and the % who receive the Brief Negotiation Interview (BNI) portion of VOICES. Counts of participants will be reported.

Practicality: Practicality will be assessed by observing the ease of VOICES use by patients. To do this, a series of steps will be watched to determine the efficiency of implementation measured by the average time (1) to consent & orient participants to the tool and (2) needed to complete VOICES documented by the Research Assistant; and (3) patients perceived time of VOICES as measured on post-survey. Each of these will be reported as part of the overall outcome. The means and standard deviations will be reported.

Efficacy of the Educational Material: To understand the efficacy of VOICES in this pilot, we will look at how many participants changed their self-identification response after completing the educational component. Counts of participants will be reported.

Efficacy of the Brief Negotiation Interview: We will look at how many patients changed their readiness to identify and readiness to disclose after completing the Brief Negotiation Interview (BNI). Counts of participants will be reported.

Efficacy of Self-Identification on Self-Disclosure: We will explore whether self-identification impacts likelihood of self-disclosure. Counts of participants who change willingness to disclose among those that self-identify will be reported.

Accuracy: To understand the accuracy of the VOICES tool, a preliminary evaluation of the accuracy of VOICES as a screening tool in correctly classifying EM cases that were positive based on social worker assessment, and those referred to Adult Protective Services (APS). The percent correct classification will be reported.

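### The SAP drops the protocol's participant-reported safety outcome (perceived safety concerns versus benefits) from Practicality and gives no reason

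*SAP*

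**What the plan says.** **Protocol.** Table 1 (section 4, Aim 2) gives Practicality three components: efficiency (times), factors affecting implementation (interruptions, wish for a caregiver to be present), and positive or negative effects "of VOICES measured by participants' perceptions of safety concerns vs. benefits as reported on post-survey". Section 10 warns that "identification of potential EM without adequate safeguards could increase the risk of physical harm, emotional harm, risk of neglect, and financial loss to the victim" and lists retaliation, loss of a caregiver, placement in a facility and distress. Section 11 adds that, for patients whose mistreatment VOICES identifies, the risk comes from the research and would be absent without it.

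**SAP.** Practicality consists of three times: to consent and orient, to complete VOICES, and as perceived by the patient. Table 1 ends its Practicality rows with "Average time patients perceived time of VOICES". Sections 4.2 and 7.2 both end the definition with the same sentence, "patients perceived time of VOICES as measured on post-survey. Each of these will be reported as part of the overall outcome", and 7.2 then asks for means and standard deviations. The Study Summary lists seven other pre-specified outcomes: acceptability, demand, practicality, three labelled efficacy, and accuracy.

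**The concern.** An outcome that the protocol made part of feasibility does not appear in the analysis plan, and the SAP does not mention or justify its removal. What remains is lopsided. The plan counts how many people changed their self-identification or readiness to disclose, but not how many of them felt that taking part raised a safety concern. For a tool meant to prompt disclosure of mistreatment, that balance belongs to the protocol's own feasibility question. It would also inform the larger multi-center study that the protocol intends to plan from these results.

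**Working it through.** The point rests on a comparison of text; neither document gives a figure for it.

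**1. Practicality, component by component**

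| Protocol Table 1 component | SAP Table 1 | SAP 4.2 | SAP 7.2 |
|---|---|---|---|
| Efficiency: three times | yes | yes | yes |
| Factors affecting implementation | no | no | no |
| Positive/negative effects | no | no | no |

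The three SAP locations agree with one another, and the Practicality text in 7.2 is complete. This is therefore not a gap in one table.

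**2. Could another SAP outcome carry it?** The nearest is Acceptability: "Participant satisfaction will be measured along multiple dimensions using post-use satisfaction survey with two 5-point Likert response set scales". One of the two scales runs from disagreement to agreement, so safety items could sit there. None is named, and the planned summary is means and standard deviations. A mean satisfaction score does not show how many people had a safety concern. Demand, the three efficacy outcomes and Accuracy do not address safety.

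**3. What the item can capture.** Protocol section 4 describes the end of the session thus: "When the older adult is finished they will signal to the RA who will collect the iPad, complete a brief post-survey". Payment and, where needed, notification of the provider are listed after that. The item therefore records perceptions at the end of the session, before the care team responds. Section 10 says that many of the named adverse events would follow the mandatory report, so the item cannot capture those.

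**4. Precision if restored.** The worst-case full width of a 95% interval for a proportion is 2 × 1.96 × √(0.25/n).

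- Protocol section 13 first: 800 × 0.057 = 45.6 and 800 × 0.0912 = 73.0, consistent with its 45 to 72. The widths are 0.29 at n = 45 and 0.23 at n = 72, in line with its stated maximum of 0.3.
- SAP section 6.1 expects 40 to 70 detected cases: 0.31 at n = 40 and 0.23 at n = 70.
- Protocol prevalences applied to the SAP's 1002: 1002 × 0.057 = 57 and 1002 × 0.0912 = 91, giving 0.26 and 0.21.
- All 1002, if every participant answered: 3.92 × √(0.25/1002) = 0.06.

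Among identified patients the result would be coarse, but about as precise as the protocol accepted for its disclosure proportions.

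**5. Adverse events.** Protocol section 12 has the principal investigator review each report to PSE and each safety admission. Section 12.1 sends serious events to the NIA and IRB within 48 hours, deaths within 24 hours, and adverse-event reports to the NIA at least semi-annually. Section 12.3, on analysis, covers feasibility outcomes only. Neither document plans a tabulation of adverse events.

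**The case against.** The strongest reply is that harm is handled outside the SAP, through the case review, expedited reporting and twice-yearly monitoring meetings of Protocol section 12. That stands. A reader might infer from the SAP that the trial has no harm information; the documents do not support this. What is missing is a planned, reported outcome.

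A reader might also infer that the SAP dropped an adverse-event analysis. It did not, because Protocol 12.3 plans none. An event table is a recommendation and not a discrepancy between the documents.

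It can also be said that the item measures perceptions, not harm. This stands too: restoring it would not show whether identified patients came to harm later.

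Finally, the survey is not in the documents. The satisfaction scale changed from 7 points in the protocol to two 5-point scales in the SAP, and the SAP (revised 3/1/2023) reports recruitment of 1002 in the past tense. The safety item may have been asked, folded into Acceptability, or left out, and an item never asked cannot now be restored. This limits the fix but leaves the omission unexplained.

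**Conclusion.** The point holds as a discrepancy between protocol and SAP: one pre-specified, participant-reported safety outcome is absent from every place where the SAP defines or analyses Practicality, while three outcomes labelled efficacy remain. It should be corrected, but the primary outcomes of participation and usage do not depend on it.

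Three further inferences go beyond the documents.

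- *That the item was removed because of its results.* The SAP gives no reason, and nothing in it points to one.
- *That harms would be diluted by reporting them over all 1002 enrolled.* Neither document proposes such a report, so no size is attached to that possibility.
- *That a count of zero events would bound the risk.* Such a bound assumes complete capture. Section 12.1 defines an adverse event as a direct result of using the tool and explicitly extends only serious events to the consequences of identification. The protocol describes one session of about 45 minutes and no participant follow-up, and leaves participants to contact the team.

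The conclusion assumes only that the SAP text is the full list of planned analyses. The widths in the working also assume that everyone in each group answers the item.

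**What to change.** **Main change.** Add the positive/negative effects outcome to Practicality in SAP Table 1, 4.2 and 7.2:

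- Summarise it in whatever response format the survey used, with n, % and 95% CI.
- Report it for all completers, and separately for those who screened positive, self-identified or disclosed.
- State that it reflects perceptions at the end of the session, before the care-team response.
- If the item was not collected, or was merged into Acceptability, say so and explain the change from the protocol.

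**Secondary recommendation.** Add one descriptive table of the adverse and serious adverse events, PSE reports and safety admissions reviewed under Protocol section 12. Show both all enrolled and EM-identified participants as denominators. Define the second group explicitly, since section 11 triggers notification on a positive screen or on a wish to disclose even when the tool is negative. State how events were ascertained and that events after discharge are likely to be under-captured.

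**Cost.** A few lines of SAP text and one or two tables. No new data collection is needed if the item was asked, because the section 12 case reviews already exist. The estimates for identified patients will be imprecise, and the event table will be incomplete for later harms and must be labelled so.

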If we also exclude subjects with clear signs of EM (1 in 24) 5%, as they will be immediately identified and reported by health care provider, then we are left with EM prevalence estimation of 5.7% - 9.12%. A sample size of eight hundred subjects (N=800) should thus result in 45-72 adults from whom we can estimate the proportions who change their self-identification response and who are ready to self-disclose after using VOICES. This will be a sufficient size to estimate a 95% confidence interval around a proportion with a width of no greater than 0.3. A sample size of 800 will provide a precision of +/- 0.14 standard deviations for the 95% confidence interval around a mean for continuous feasibility outcomes (e.g. acceptability, time to completion). This sample size will also produce precision of no worse than +/- 14% in the estimation of a 95% confidence interval around a proportion for dichotomous feasibility outcomes (e.g. demand, implementation).

SECTION II: RESEARCH INVOLVING DRUGS, BIOLOGICS, RADIOTRACERS, PLACEBOS AND DEVICES

If this section (or one of its parts, A or B) is not applicable, check off N/A and delete the rest of the section.

A. RADIOTRACERS **N/A**

B. DRUGS/BIOLOGICS **N/A**

B. DEVICES **N/A**

SECTION III: RECRUITMENT/CONSENT AND ASSENT PROCEDURES

1. Targeted Enrollment: Give the number of subjects:

- Targeted for enrollment at Yale for this protocol: 800
- If this is a multi-site study, give the total number of subjects targeted across all sites:

2. Indicate recruitment methods below. Attach copies of any recruitment materials that will be used.

VOICES Feasibility Study:

 Flyers	 Internet/web postings	 Radio
 Posters	 Mass email solicitation	 Telephone
 Letter	 Departmental/Center website	 Television
 Medical record review*	 Departmental/Center research boards	 Newspaper
 Departmental/Center newsletters	 Web-based clinical trial registries	 Clinicaltrials.gov
 YCCI Recruitment database	 Social Media (Twitter/Facebook):	

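### The SAP asks whether self-identification affects self-disclosure, but measures disclosure only among self-identifiers, as a level in one place and a change in others, with no comparison with non-identifiers

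*SAP*

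**What the plan says.** The question is in SAP 4.2 and is repeated in 7.2: "We will explore whether self-identification impacts likelihood of self-disclosure".

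Three measures are attached to it:

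- SAP Table 1 (section 4): "Measured as % of patients who disclose among those who self-identified (O". The closing letter is the table's code for an other pre-specified outcome. This is a level.
- SAP 4.2: "Effect-size estimation measured by change in the % of patients who disclose among those who self-identified". This is a change, in percentage terms.
- SAP 7.2: "Counts of participants who change willingness to disclose among those that self-identify will be reported". This is a count of changers, with no denominator or interval named.

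Protocol Table 1 (Limited Efficacy) lists an "exploration of whether self-identification impacts likelihood of self-disclosure". Under a separate label it lists an effect size "measured by change in the % of patients who disclose". Neither entry is split by self-identification.

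Protocol item 13 (Statistical Considerations, VOICES Feasibility Study) expects "45-72 adults from whom we can estimate the proportions who change their self-identification response and who are ready to self-disclose" after using VOICES.

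The Protocol's Screening/Data Collection Description describes the flow twice. The first account says: "For participants who screen positive, VOICES will ask them if they would like to self-disclose". Those who agree stop there; those who decline complete the Brief Negotiation Interview (BNI) and are asked again. The second account speaks only of being asked to self-identify, before and after the BNI. A choice to identify is then relayed by the research assistant to the care team as a wish to disclose.

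**The concern.** Whether one answer affects the likelihood of another can be judged only by comparing the second answer across values of the first. All three measures hold self-identification fixed at yes. Whatever they show, a reader learns nothing about disclosure among those who did not self-identify, and so nothing about whether self-identification matters.

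Two consequences follow. The effect-size wording in 4.2 invites a claim that the planned output cannot support. And because Table 1 gives a level while 4.2 and 7.2 give a change, two reports could each follow the SAP under the same outcome name and differ severalfold.

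No primary result depends on this. What is at stake is how one of the seven other pre-specified outcomes is interpreted.

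**Working it through.** **1. The plan's nearest figure reproduces, but it is for a single proportion.** Protocol item 13 gives N = 800 and prevalence 5.7% to 9.12%. Then 800 × 0.057 = 45.6 and 800 × 0.0912 = 72.96, which match the stated 45 to 72 after truncation. The full Wald 95% width at p = 0.5 and n = 45 is 2 × 1.96 × √(0.25/45) = 0.292, within the stated 0.3. This says nothing about the precision of a difference between two groups.

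**2. The measures are all conditional on self-identifying.** Table 1, 4.2 and 7.2 carry the same restriction. Neither document gives the disclosure proportion in non-identifiers, or a difference, ratio, model or test by self-identification. The only between-group tests named (Protocol Table 1) concern demographic differences. The Protocol's subgroup interest, in its outcome-analysis text, is in sex, age, weight and health conditions.

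**3. The same output fits opposite answers (hypothetical).** Suppose 50% of self-identifiers disclose. If non-identifiers disclose at 10%, 50% or 70%, the difference is 50 − 10 = +40, 50 − 50 = 0 or 50 − 70 = −20 points. The planned output is identical in all three cases.

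**4. Level and change diverge (hypothetical).** Take 40 self-identifiers, of whom 20 agree when first asked and 5 more after the BNI, and assume that change means first answer versus answer after the BNI.

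| Place | Reported |
|---|---|
| Table 1 | 25/40 = 62.5% (or 20/40 = 50% at the first answer) |
| 4.2 | 62.5 − 50 = +12.5 points |
| 7.2 | 5 people (5/40 = 12.5%) |

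The time points in this example are assumed; the SAP states none. In the Protocol's first account of the flow, the only repeat of the disclosure question comes after the BNI. On that reading the 7.2 count is part of the separate BNI outcome, which already counts changed readiness to disclose.

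**5. Precision of the missing comparison.** Wald half-width = 1.96 × √(0.25/n₁ + 0.25/n₂), with p = 0.5 in both groups. The share who self-identify is not given, so splits of 50:50 to about 30:70 are assumed.

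| People asked | Equal split | About 30:70 |
|---|---|---|
| 40 (SAP 6.1, lower) | 20/20: 0.310 | 12/28: 0.338 |
| 45 (Protocol, lower) | 22/23: 0.292 | 14/31: 0.316 |
| 70 (SAP 6.1, upper) | 35/35: 0.234 | 21/49: 0.256 |
| 72 (Protocol, upper) | 36/36: 0.231 | 22/50: 0.251 |
| 75 | 37/38: 0.226 | 22/53: 0.249 |
| 120 | 60/60: 0.179 | 36/84: 0.195 |

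The first four rows treat everyone asked as a true case. Those asked would include false-positive screens. If 60% of those asked were true cases (assumed) and every case screened positive, 45 to 72 cases would imply 45/0.6 = 75 to 72/0.6 = 120 people asked. The SAP reports 1,002 recruited; at the Protocol's prevalences that is 1,002 × 0.057 = 57 to 1,002 × 0.0912 = 91 cases, so precision could be somewhat better than the N = 800 figures suggest.

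**6. Confounding by true mistreatment (all inputs assumed).** Let 60% of those asked be true cases. Let 80% of true and 10% of false positives self-identify. Let 50% of true and 0% of false positives disclose, whether or not they self-identify. Identifiers: 0.6 × 0.8 + 0.4 × 0.1 = 0.52, of whom 0.24 disclose, so 46.2%. Others: 0.48, of whom 0.06 disclose, so 12.5%. The difference is 33.7 points although identifying has no effect.

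**The case against.** The strongest reply is that this is a feasibility study. The Protocol calls the analysis primarily descriptive, places this item among observed trends and says that efficacy is not the objective. That stands, and it limits the importance. It does not rescue the measure, because even a descriptive answer to this question needs two groups.

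It can also be said that 4.2 does plan a contrast, namely a change within self-identifiers. That is correct, so it would be too broad to say that no contrast of any kind is planned. But this change does not vary self-identification, and its time points are undefined. For the same reason, a reader should not treat the changes in 4.2 and 7.2 as certainly one quantity on two scales.

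Two stronger readings are tempting and are not supported:

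- *That the SAP dropped a comparison the Protocol had planned.* The Protocol's effect size and its expected 45 to 72 adults are not limited to self-identifiers, but the Protocol never planned a comparison by self-identification either.
- *That disclosure among self-identifiers is 100% by construction.* This rests on the research assistant's spoken message to the care team, which is not a data definition. The Protocol's outcome-analysis text lists self-identification and self-disclosure as separate responses, and SAP 4.2 and 7.2 separate readiness to identify from readiness to disclose. The Protocol's Background on the BNI also fits the account in which people who screen positive are asked about disclosure.

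Finally, a comparison with non-identifiers would be imprecise and confounded, and would be added late. All three points stand, and they govern how it should be labelled.

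**Conclusion.** The point holds for the SAP as written. Its question concerns the effect of self-identification on disclosure, every measure is confined to self-identifiers, and no comparison with non-identifiers is planned in either document. Following the plan exactly cannot answer the question, the effect-size wording has no support, and a level and a change share one outcome name.

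The importance is minor to moderate, because the outcome is exploratory and non-primary and no primary analysis is touched. That conclusion rests on the wording alone. The percentages in the illustrations are hypothetical, and the precision figures depend on the assumed splits, on 50% disclosure in both groups and on how many people were asked. The available text does not fully settle who was asked: the flow chart (Figure 3) is not visible here, and the Protocol leaves the exact question wording to the development stage.

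**What to change.** Use one definition in Table 1, 4.2 and 7.2. First confirm that everyone who screened positive was asked about disclosure and that the answer was recorded separately from self-identification. Reconcile this with the second account in the Protocol's Screening/Data Collection Description.

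- **If confirmed:** among all who were asked the disclosure question, cross-tabulate self-identification (after the education, before the BNI) by the first disclosure answer (before the BNI). Report n/N with a 95% CI in each group, and the risk difference with a Newcombe 95% CI. Describe it as an exploratory, non-randomised association that may reflect true mistreatment status. The SAP summary, revised 3/1/2023, already reports 1,002 recruited and an average session of 8.8 minutes, so date the comparison and label it as added after recruitment.
- **If non-identifiers were not asked, or the two answers were not recorded separately:** remove the wording about impact on likelihood and about effect size, and report only the descriptive rate (n/N, Wilson 95% CI).

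The cost is SAP wording and, in the first case, one 2x2 table from answers the tool records. The downside in the first case is a wide interval (Wald half-width about 0.23 to 0.34 if 40 to 72 people were asked, about 0.18 to 0.25 if 75 to 120 were) and confounding by true mistreatment status. In the second case the question is withdrawn, not answered.
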